### 2.2.2. Study rationale for Part B

**The purpose of Part B is to evaluate the safety and Day 29 immunogenicity of CV0801 under 3 different storage conditions.**

## 2.3. Benefit/risk assessment

### 2.3.1. Risk assessment

Detailed information about the known and expected risks of the CV0601, CV0701, **and CV0801** vaccines is provided in the Investigator's Brochure (IB). Important potential risks are the following:

- Hypersensitivity reactions, including anaphylaxis
- Myocarditis
- Pericarditis

To mitigate these important potential risks, the following risk mitigation strategies have been included in the protocol:

- All participants will remain under observation at the vaccination center for at least 30 minutes after vaccination.
- Individuals with history of hypersensitivity or severe allergic reaction to any previous mRNA vaccine or any component of the study intervention(s) are excluded from the study enrollment, and participants will be instructed to contact the study site immediately for occurrence of any possible hypersensitivity reaction within 1 day of vaccination.
- Individuals at increased risk of myocarditis or pericarditis and individuals with a history of myocarditis or pericarditis are excluded from the study enrollment. All participants will be educated on the symptoms of myocarditis and pericarditis and will receive guidance on contacting study personnel and seeking medical care if any of these symptoms occur. Any participants with suspected myocarditis or pericarditis within 6 weeks after study intervention administration will be referred to a cardiologist by the investigator for diagnosis and management. A safety follow-up will be ensured until resolution of symptoms and/or abnormal test findings.
- Anaphylaxis or severe hypersensitivity within 24 hours after study intervention administration, myocarditis and pericarditis will be collected as adverse events of special interest (AESIs).
- Participants will receive close medical monitoring and medical assessments during the study per the Schedule of Activities (SoA) ([Table 1](#) and [Table 2](#)).

In addition, vasovagal syncope and other anxiety related reactions as a psychogenic response to the needle injection can occur following or even before any vaccination. Therefore, all participants will remain under observation at the vaccination center for at least 30 minutes after the vaccination.

The potential risks associated with the investigational vaccines are considered acceptable, considering the measures planned to minimize risk to participants in this study and experience from the Phase 1 study with CV0501, the monovalent modified-nucleoside mRNA vaccine encoding an **CCI** spike protein using the **CCI** as CV0601, CV0701, **and CV0801** (see Section [4.3](#)).

*Whilst the June 2022 VRBPAC recommended a bivalent vaccine encoding the Original and CCI [REDACTED]*, a monovalent vaccine encoding the CCI [REDACTED]

CCI [REDACTED] is also included in the original study (Part A) to evaluate specific scientific objectives that cannot be met with bivalent vaccines alone. It is not anticipated that the participants randomized to the monovalent vaccine cohort will be disadvantaged compared to their bivalent counterparts, and there is scientific equipoise between all groups.

Refer to the Prescribing Information or Summary of Product Characteristics for expected adverse reactions associated with CCI [REDACTED] [[Summary of product characteristics](#); [Prescribing information](#)].

### **2.3.2. Benefit assessment**

Participants are not expected to directly benefit from study participation. However, their participation in this study will contribute to generating information regarding the safety and immunogenicity of the vaccine.

Additionally, study participants may benefit from gaining information about their general health status through the medical evaluations/assessments associated with this study (i.e., physical examination).

### **2.3.3. Overall benefit/risk conclusion**

Considering the measures taken to minimize risk to participants in this study and given the accumulation of favorable safety/immunogenicity data from the Phase 1 study of CV0501 (see Section 4.3), the potential risks are justified by the anticipated benefits linked to the development of the investigational vaccines CV0601, CV0701, **and CV0801**.

### 3. OBJECTIVES, ENDPOINTS, AND ESTIMANDS

**Table 5      Objectives and endpoints for Part A**

Primary Objectives	Primary Endpoints (population summary)
To compare the immunogenicity of CV0701 and CV0601 booster vaccines with CCI [REDACTED] CCI [REDACTED] at Day 29	
 
Serum neutralization titers against pseudovirus bearing specific CCI [REDACTED] spike protein at Day 29 (GMT)
 
Serum neutralization titers against pseudovirus bearing specific CCI [REDACTED] spike protein at Day 29 (GMT)
 

To evaluate the safety and reactogenicity of CV0701 and CV0601 booster vaccines	
 
Occurrence of solicited administration site and systemic AEs within 7 days (i.e., from Day 1 to Day 7 included) of study intervention administration (percentage of participants)
 
Occurrence of unsolicited AEs within 28 days (i.e., from Day 1 to Day 28 included) of study intervention administration (percentage of participants)
 
Occurrence of MAAEs, SAEs and AESIs from Day 1 through the end of the study (approximately 180 days after the study intervention administration), each summarized separately (percentage of participants)
 

Secondary Objective	Secondary Endpoints (population summary)
To compare the immunogenicity of CV0701 and CV0601 booster vaccines with CCI [REDACTED] CCI [REDACTED] CCI [REDACTED]	
 
Serum neutralization titers against pseudovirus bearing specific CCI [REDACTED] spike protein at Day 91 and Day 181 (GMT)
 
Serum neutralization titers against pseudovirus bearing specific CCI [REDACTED] spike protein at Day 91 and Day 181 (GMT)
 
Serum neutralization titers against pseudovirus bearing specific CCI [REDACTED] spike protein at Day 29, 91 and Day 181 (GMT)
 
Seroresponse* from baseline of serum neutralization titers against pseudovirus bearing specific CCI [REDACTED] spike protein at Day 29 (percentage of participants)
 
Seroresponse* from baseline of serum neutralization titers against pseudovirus bearing specific CCI [REDACTED] CCI [REDACTED] spike protein at Day 29 (percentage of participants)
 
Seroresponse* from baseline of serum neutralization titers against pseudovirus bearing specific CCI [REDACTED] spike protein at Day 29 (percentage of participants)
 
Fold increase from baseline of serum neutralization titers against pseudovirus bearing specific CCI [REDACTED] spike protein at Day 29, Day 91, and Day 181 (GMI)
 
Fold increase from baseline of serum neutralization titers against pseudovirus bearing specific CCI [REDACTED] CCI [REDACTED] spike protein at Day 29, Day 91, and Day 181 (GMI)
 
Fold increase from baseline of serum neutralization titers against pseudovirus bearing specific CCI [REDACTED] spike protein at Day 29, Day 91, and Day 181 (GMI)
 

CCI

AE: adverse event; AESI: adverse events of special interest; GMI: geometric mean increase; GMT: geometric mean titer; IgG Ab: immunoglobulin G antibody; MAAE: medically attended adverse event; mRNA: messenger ribonucleic acid; RT-PCR: reverse transcriptase polymerase chain reaction; SAE: serious adverse event; SARS-CoV-2: severe acute respiratory syndrome coronavirus 2

\* CCI

CCI

**Table 6      Objectives and endpoints for Part B**

Primary Safety Objective	Primary Safety Endpoints (population summary)
To evaluate the safety and reactogenicity of three CV0801 booster vaccine manufacturing specifications	
Solicited events:
 
 
Occurrence of solicited administration site and systemic AEs within 7 days (i.e., from Day 1 to Day 7 included) of study intervention administration (percentage of participants)
 
 
Unsolicited events:
 
 
Occurrence of unsolicited AEs within 28 days (i.e., from Day 1 to Day 28 included) of study intervention administration (percentage of participants)
 
 
SAEs, AESIs and MAAEs:
 
 
Occurrence of MAAEs, SAEs and AESIs from Day 1 through the end of the study (approximately 180 days after the study intervention administration), each summarized separately (percentage of participants)
 

Primary Immunogenicity Objective	Primary Immunogenicity Endpoint
To evaluate the immunogenicity of three CV0801 booster vaccine manufacturing specifications	
 
Serum neutralization titers against pseudovirus bearing specific CCI spike protein at Day 29 (GMT)
 

AE: adverse event; AESI: adverse events of special interest; GMT: geometric mean titer; MAAE: medically attended adverse event; SAE: serious adverse event

Complementary details on estimands such as impact of intercurrent events is provided in Section 9.

## 4. STUDY DESIGN

### 4.1. Overall design

#### 4.1.1. Overall study design of Part A

**Part A of the randomized**, observer-blind Phase 2 study will evaluate the safety, reactogenicity and immunogenicity of a single booster dose of CV0701 and CV0601 compared to CCI CCI in healthy adults who have previously received a complete primary vaccination series with or without booster dose(s). Multiple dose strengths of CV0701 will be evaluated. Participants will be randomized equally across 5 arms, which will include CCI CCI CCI to serve as a standard of care control). An overview of the study design is provided in Section 1.2, Figure 1.

There are 2 investigational products in **Part A** (see also Section 6.1, Table 7):

1. CV0601, a monovalent modified-nucleoside mRNA COVID-19 vaccine encoding CCI spike protein.
2. CV0701, a bivalent modified-nucleoside mRNA COVID-19 vaccine encoding spike proteins: 1) CCI (CV0801) and 2) CCI (CV0601).

CCI

CCI [REDACTED]. The mRNA is encapsulated in LNPs CCI [REDACTED]  
CCI [REDACTED] which enhance mRNA uptake into the cells where the mRNA is translated into antigen. CCI [REDACTED]

CCI [REDACTED]. The bivalent vaccine CV0701 will be presented as 2 separate components in glass vials. These components will be mixed in a separate 10 mL vial prior to administration according to directions provided in the Pharmacy Manual.

**Comparator:** CCI [REDACTED]

CCI

#### **4.1.2. Overall design of Part B**

*Part B of the randomized and observer-blind Phase 2 study will evaluate the safety, reactogenicity and immunogenicity of CV0801 (a monovalent modified-nucleoside mRNA COVID-19 vaccine encoding CCI [REDACTED] spike protein) under 3 different storage conditions in healthy adults who have previously received a complete primary vaccination series with or without booster dose(s). Participants will be randomized equally across 3 arms:*

- *Condition 1: CV0801 CCI [REDACTED] baseline-control*
- *Condition 2: CV0801 CCI [REDACTED] intermediate storage conditions*
- *Condition 3: CV0801 CCI [REDACTED] maximum storage conditions*

*Condition 1 clinical trial material will serve as the baseline-control from which safety, reactogenicity and immunogenicity of Condition 2 and 3 (intermediate and maximum storage conditions) materials will be compared.*

*An overview of the study design is provided in Section 1.2, Figure 2.*

Details on safety monitoring by the Independent Data Monitoring Committee (IDMC) and internal Data Review Committee (iDRC) are provided in Section 8.5 for both parts of the study.

This study will be conducted by a contract research organization (CRO; PPD, part of Thermo Fisher Scientific).

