### 4.2.2. Scientific rationale for study design for Part B

*mRNA vaccine stability is affected by product-specific characteristics (such as molecular weight, buffer, lipid nanoparticle [LNP] encapsulation, etc), manufacturing processes-specific characteristics such as the length of time the vaccine is in liquid form (either during manufacturing, fill and finish, or during preparation and handling of the vaccine at different temperatures), and storage conditions of the finished product.*

*The effect of these manufacturing and storage conditions on the final attributes of the vaccine is mainly derived from product and process knowledge and from clinical experience collected throughout all phases of product development.*

**Through this Part B of the Phase 2 study, the Companies (GSK and CureVac) aim to develop data on products stored at different conditions within a clinical trial setting. In doing so, this amendment will compare the safety, reactogenicity, and Day 29 immunogenicity of 2 specifications of booster dose investigational COVID-19 mRNA vaccines exposed to storage conditions.**

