### 9.3.2. Primary endpoints analysis

The group GMT ratio associated 2-sided 95% CI and p-value for the null hypothesis that group GMT ratio is below 0.67 will be based on group contrast from an ANCOVA model on  $\log_{10}$ -transformed anti-neutralizing titer. The model will include the vaccine group, country, previous known COVID-19 infection (yes, defined by self-reporting or positive N protein at pre-vaccination, no), age (< 65 years,  $\geq$  65 years), and  $\log_{10}$ -transformed pre-dose titer as fixed effects. For this model, a titer below a quantifiable threshold will be assigned half the threshold while a titer above a quantifiable threshold will be assigned the threshold.

The primary safety endpoints as detailed in **Table 5 for Part A** and **Table 6 for Part B** will be analyzed as described in the SAP. For all reactogenicity and other safety endpoints, descriptive summary statistics will be provided for the Diary set and ES, respectively.

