### **4.2. Primary Endpoint(s) Analyses**

#### **4.2.1. Safety and reactogenicity endpoints**

For Part A and Part B separately, reactogenicity descriptive summary statistics will be provided for the eDiary Set by vaccine group; other safety endpoints, descriptive summary statistics will be provided for the ES.

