##### **4.2.1.1. Solicited AEs**

All solicited events must be recorded into the eDiary by the participant during the first 7 days following administration of the dose of study intervention (Day 1 to Day 7 included), irrespective of occurrence or intensity. Solicited events ongoing after Day 7 will be recorded in the eCRF and followed-up until the event has resolved, subsided, stabilized, disappeared, or until the event is otherwise explained, the participant is lost to follow up, or study is completed. If the collection of solicited AEs was not possible for any reasons via the eDiary and solicited AEs were reported to the investigator by the participant, then it would be possible for them to be reported directly to the site staff and submitted (e.g., via the eCRF).

The following administration site events will be solicited:

- a. Pain
- b. Redness
- c. Swelling
- d. Lymphadenopathy, defined as localized axillary, cervical or supraclavicular swelling or tenderness ipsilateral to the injection arm

The following systemic events will be solicited:

- e. Fever
- f. Chills
- g. Headache
- h. Fatigue

- i. Myalgia
- j. Arthralgia

Note: Participants will be instructed to measure and record the axillary temperature in the evening. If additional temperature measurements are taken at other times of the day, participants will be instructed to record the highest temperature in the eDiary.

Grading or actual temperature/redness and swelling will be captured in the eDiary as per a modified grading of symptoms based on the FDA toxicity grading guidance for industry [FDA, 2007] with Grades 3 and 4 combined and swelling evaluated using the actual measurement only (refer to Section 6.2.2.2). When solicited AE data entered by the participant are missing or incorrect, data collected by study investigator/staff will be used in the summaries if available.

The percentage of participants reporting each individual solicited administration site event (any grade, Grade 1, Grade 2, Grade 3, any grade ongoing at day 7 and medically attended events) and solicited systemic event (any grade, Grade 1, Grade 2, Grade 3, any grade ongoing at day 7 and medically attended events) within the 7-day follow up period (i.e., Day 1-Day 7 post-dosing) will be tabulated for each group.

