#### **4.2.1.2. Unsolicited AEs with onset within the 28 days follow-up period (day 1-28)**

An AE is any untoward medical occurrence in a clinical study participant, temporally associated with the use of a study intervention, whether or not considered related to the study intervention. An AE can therefore be any unfavorable and unintended sign (including an abnormal laboratory finding), symptom, or disease (new or exacerbated) temporally associated with the use of a study intervention.

The verbatim reports of unsolicited AEs will be reviewed by a qualified person and the signs and symptoms will be coded according to the Medical Dictionary for Regulatory Activities (MedDRA) Dictionary for Adverse Reaction Terminology. Every verbatim term will be matched with the appropriate PT.

A study intervention causally related AE is defined as an AE for which the investigator classifies the possible relationship to study intervention as “Yes”. Investigators will not be required to assess the causality of solicited Aes if the onset is during the solicitation period.

The investigator is obligated to assess the relationship between study intervention and each occurrence of each AE/SAE/. The investigator will use clinical judgment to determine the relationship.

The percentage of participants with any unsolicited Aes within the 28-day follow up period (i.e., Day 1-Day 28) with its exact 95% confidence interval (CI) will be tabulated by group and by MedDRA PT and System Organ Class (SOC). Similar tabulation will be done for Grade 3 unsolicited Aes, for any causally related unsolicited Aes, for Grade 3 causally related unsolicited Aes, for unsolicited Aes resulting in a medically attended visit and for SAE.

A data listing for all unsolicited AEs will be provided by age group (< 65 years,  $\geq$  65 years), dose group and participant number.

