#### **4.2.1.3. MAAEs, SAEs and AESIs with onset after vaccination (day1 up to study end)**

The study will capture the following specific over the full study period: MAAE, SAE and AESIs defined as either :

- Potential immune-mediated disorders (pIMDs),
- Any laboratory-confirmed moderate to severe case of COVID-19,
- Myocarditis and pericarditis and,
- Anaphylaxis or severe hypersensitivity within 24 hours after study intervention administration.

All suspected cases of COVID-19, myocarditis, and pericarditis in study participants will be diagnosed and clinically evaluated, which may require unscheduled study site visits and additional testing based on the investigator’s judgment.

The number and percentage of participants with any event for each MAAE, SAE, AESI In addition, summary will be provided by relationship to study intervention, maximum grade/severity and outcome. The worst-case approach will be applied at participant level for the maximum grade/severity, i.e., a participant will only be counted once as the worst case from all the events experienced by the participant.

The percentage of participants with at least 1 report of SAE (any, related, fatal and fatal related), with at least 1 report of MAAE and with at least 1 report of AESI, respectively,

classified by the MedDRA SOC and PT and reported from Dose 1 up to study end will be tabulated with exact 95% CI.

In the AESI/SAE summaries, a participant with 2 or more Aes within the same SOC or PT level but different relationship will be counted only once in the level using the related incident.

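### Part B says it will compare safety and reactogenicity of Conditions 2 and 3 with Condition 1, but no between-condition estimate with a confidence interval is specified for any safety endpoint

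*Protocol*

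**What the plan says.** **Where a comparison is promised.** Protocol 4.1.2 makes Condition 1 the reference for all three domains: it "will serve as the baseline-control from which safety, reactogenicity and immunogenicity of Condition 2 and 3" will be compared. Protocol 4.2.2 says "this amendment will compare the safety, reactogenicity, and Day 29 immunogenicity of 2 specifications" of the booster. Protocol 4.3 adds that Part B should give exploratory data on changes in reactogenicity, safety and immunogenicity caused by reduced stability.

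**The objective.** Protocol Table 6 words the primary safety objective as "To evaluate the safety and reactogenicity of three CV0801 booster vaccine manufacturing specifications", with percentages of participants as the population summary. The primary immunogenicity objective uses the same verb.

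**What is planned for safety.**
- Protocol 9.3.2: "descriptive summary statistics will be provided for the Diary set and ES, respectively".
- SAP 4.2.1: "reactogenicity descriptive summary statistics will be provided for the eDiary Set by vaccine group", with descriptive summaries on the Exposed Set for the other safety endpoints.
- SAP 4.2.1.1: the percentage with each individual solicited event, by grade, "within the 7-day follow up period (i.e., Day 1-Day 7 post-dosing) will be tabulated for each group". No CI is mentioned.
- SAP 4.2.1.2: unsolicited AEs by group, with exact 95% CIs.
- SAP 4.2.1.3: SAEs, MAAEs and AESIs "reported from Dose 1 up to study end will be tabulated with exact 95% CI".
- SAP 4.6: a by-group table of solicited and unsolicited AEs excluding SAEs, with exact 95% CIs.

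**What is planned for immunogenicity.** SAP 2 and 4.2.2 define the GMT ratio of Conditions 2 and 3 over Condition 1 with a 95% CI. SAP 4.2.2 also gives a Miettinen-Nurminen CI for a difference in seroresponse rates.

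**The concern.** A single sentence in Protocol 4.1.2 promises a comparison in three domains, and only one of them receives a between-arm estimate. Any effect of storage on reactogenicity is a randomised contrast, so the quantity that answers the question is a difference between arms. Percentages set side by side, or intervals for each arm separately, do not report that difference or its uncertainty.

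A recommendation draws on these data. SAP 1.2 has the unblinded iDRC review Day 29 safety and immunogenicity data and, for Part B, make a recommendation on storage condition for a future Phase 3 study. Similar-looking columns could then be taken as showing no change when the data do not exclude a sizeable increase or decrease.

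**Working it through.** **Inputs.** 83 participants per group, 1:1:1, total 249 (Protocol 9.5.2, SAP 5); 95% confidence level (SAP 2). The documents give no expected event rates, so every rate below is an assumption.

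**The plan's own figure.** 3 × 83 = 249, which agrees. The rest of the sample size justification is blacked out and is not questioned here.

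**Step 1: what is specified.**

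| Domain | Per-arm estimate | Per-arm CI | Between-arm estimate with CI |
|---|---|---|---|
| Day 29 titer | adjusted GMT | yes | GMT ratio against Condition 1 |
| Solicited events, per event and grade (SAP 4.2.1.1) | percentage | none stated | none |
| Unsolicited AEs (SAP 4.2.1.2) | percentage | exact | none |
| SAEs, MAAEs, AESIs (SAP 4.2.1.3) | percentage | exact | none |
| Solicited and unsolicited AEs excluding SAEs (SAP 4.6) | percentage | exact | none |

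The text of SAP 4.2.1 and 4.6 has no blacked-out part that could hold a safety contrast. SAP 6.2.3.2 sets decimals for differences in percentages, but it is a formatting rule and is not tied to any safety analysis.

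**Step 2: approximate precision of a difference.** With a common rate p in both arms, the 95% half-width is 1.96 × √(2p(1−p)/83):
- p = 0.10: 1.96 × √(0.18/83) = 0.091
- p = 0.30: 1.96 × √(0.42/83) = 0.139
- p = 0.60: 1.96 × √(0.48/83) = 0.149

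**Step 3: the interval the SAP already uses for seroresponse.** The Miettinen-Nurminen interval contains every δ for which (p̂₁ − p̂₂ − δ)² / V(δ) ≤ 1.96². Here V(δ) is the variance of the difference at the maximum-likelihood rates restricted to difference δ, multiplied by N/(N−1) with N = 166. For equal observed counts:
- 4/83 in each arm (4.8%): −7.4 to +7.5 points
- 8/83 (9.6%): −9.4 to +9.5
- 42/83 (50.6%): −15.1 to +15.1
- 58/83 (69.9%): −14.1 to +14.1

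**Step 4: why per-arm intervals do not replace the contrast.** Suppose 50/83 (60.2%) in one arm and 42/83 (50.6%) in Condition 1. The exact per-arm CIs are 48.9 to 70.8 and 39.4 to 61.8. The difference is 8/83 = 9.6 points, with 95% CI −5.5 to 24.4. These data fit a small decrease or an increase of about 24 points, and no planned safety output would show that range.

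**The case against.** The strongest reply is that the objective governs. Table 6 asks only that safety be evaluated, by percentage of participants, and the by-group tables deliver that. The study is declared descriptive, without hypothesis tests or type 1 error adjustment (SAP 2 and 2.1). Randomised arms tabulated beside a named control are a comparison of a kind, and unblinded committees review the data. Anyone can compute a difference from the tabulated counts, and intervals of this width would seldom settle the matter.

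Much of this stands. A reader might infer that the promised comparison is not made at all, or that the plan offers nothing beyond bare percentages. The documents do not support either reading: side-by-side randomised percentages are an informal comparison that fits Table 6, and exact per-arm CIs are planned for most safety summaries, including a SAP 4.6 table that covers solicited events. Nor can one infer that a test or a safety margin is missing, or that the sponsor plans to conclude there is no change. No passage sets a safety margin or announces such a conclusion; the 0.67 threshold applies to immunogenicity only.

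What does not stand is the verb as an explanation. Table 6 also says evaluate for immunogenicity, which still gets a ratio with a CI inside the same descriptive framework. SAP 2 puts the emphasis on estimation with 95% CIs, and a risk difference with a CI is exactly that. That the intervals are wide is a reason to show them.

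**Conclusion.** The point holds as a gap in specification. Protocol 4.1.2 and 4.2.2 promise a comparison of safety and reactogenicity, and the plan specifies no between-condition estimate with a CI for any safety endpoint. The solicited tables by event and grade lack even per-arm intervals. No planned analysis is wrong and no stated number is contradicted.

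The uncertainty left unreported is about ±9 points at a 10% event rate and about ±15 points at 50% to 60%. These figures assume the event rates and a full 83 per arm; a smaller eDiary Set would widen them.

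**What to change.** In SAP 4.2.1, for Part B, add two differences in percentages, Condition 2 minus Condition 1 and Condition 3 minus Condition 1, with two-sided 95% Miettinen-Nurminen CIs, for this prespecified list:
- any, and any Grade 3, solicited administration-site event (at least one event in the category, eDiary Set);
- any, and any Grade 3, solicited systemic event (same rule, eDiary Set);
- any unsolicited AE (Exposed Set).

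State that the estimates are descriptive, with no margin and no multiplicity adjustment, and that an interval including zero does not show absence of change.

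**Cost.** No new data are needed, and the method and SAS option are already in SAP 4.2.2 for seroresponse. Three small costs should be accepted openly. The category-level composites must be derived, because SAP 4.2.1.1 tabulates individual events. The code must be run pairwise against Condition 1. The table will hold 5 endpoints × 2 contrasts = 10 wide, unadjusted intervals, of which about 10 × 0.05 = 0.5 would exclude zero by chance if storage had no effect.

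**Alternative.** If the sponsor does not want the contrast, reword Protocol 4.1.2 and 4.2.2 to say that safety and reactogenicity are described by group alongside Condition 1. Either change brings the design text and the analysis into line.
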